Name of the principal investigator at the sub-center:

Signature: Date: Year Month Day

Signature: Date: Year Month Day

Sponsor/Lead Organization

corporate name		Changzheng Hospital Affiliated to Naval Medical University	
project leader		[name]	
Contact address	[name]	zip code	200003
[contact]	cellphone	[name]
portraiture	[name]	E-mail	[contact]

Cooperative Unit

Company/Unit Name		Innovent Biologics (Suzhou) Co., Ltd.	
project leader			
Contact address		zip code	
telephone		cellphone	
portraiture		E-mail	

Company/Unit Name		Chia Tai Tianqing Pharmaceutical Group Co., Ltd.	
project leader			
Contact address		zip code	
telephone		cellphone	
portraiture		E-mail	

scenario summary	
scenario name	A phase II study of anlotinib plus sintilimab as first-line treatment for advanced non-liver metastatic colorectal cancer
Program number	APICAL-CRC2
version number	1.0
date	2025-12-8
Sponsor	Shanghai Changzheng Hospital
indication	Advanced colorectal cancer
Estimated study duration	The study is scheduled from December 2025 to December 2026. Enrollment for this research project is planned to commence in December 2025 and is expected to conclude in December 2026. Data analysis will be completed in June 2026, with the total trial duration approximately 1.5 years.
purpose of research	The efficacy of anlotinib combined with sintilimab as first-line therapy for advanced non-hepatic metastatic colorectal cancer was evaluated using the investigator-assessed objective response rate (ORR).
Total number of cases	The sample size calculation was based on the margin of confidence compared with historical controls, assuming an ORR of 70% in this study and an ORR rate of 50% in the historical controls. In the ITT analysis set, according to the Simon two-stage design, with a one-sided $\alpha=0.05$ and statistical power=0.8, the calculated sample size was 37 cases.

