3.7.1 Efficacy Indicators

Objective response rate (ORR) refers to the proportion of patients whose tumors shrink to a certain extent and sustain this reduction for a specified duration (primarily for solid tumors). It encompasses cases of complete response (CR) and partial response (PR).

Deepness of response (DpR): This refers to the percentage of maximum tumor shrinkage achieved during treatment compared to baseline. If a complete response (CR) is observed, the DpR is 100%.

Tumor response and disease progression will be assessed by investigators according to the RECIST criteria.

Progression-free survival (PFS) refers to the time from enrollment until tumor progression or death.

Overall survival (OS) refers to the time from randomization to death from any cause.

The duration of response maintenance was calculated for all patients who achieved confirmed RECIST-standardized PR or CR. The response maintenance period was defined as the time from the first recorded PR or CR until death or disease progression (whichever occurred first). For patients who were still alive and disease-free as of the analysis date, the cutoff date was set as the date of their last radiological assessment.

This study also explores the relationship between molecular markers and therapeutic efficacy and safety.

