5.1 Statistical and Analysis Plan

5.1.1 Study Population Analysis

The efficacy analysis will be conducted in the intention-to-treat (ITT) population, defined as all patients who received at least 2 cycles of study drug therapy. The safety analysis population includes all patients who received at least one dose of study drug therapy. The response rate analysis population refers to all patients in the ITT population who achieved partial or complete response as determined by the RECIST criteria.

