5.1.3 Efficacy Analysis

The efficacy analysis will be performed in the ITT population.

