5.1.3.1 Primary Efficacy Analysis

The primary endpoint was the objective response rate (ORR). The objective response rate refers to the proportion of patients who achieved tumor shrinkage of a certain size and maintained it for a specified duration, including cases with complete response (CR) or partial response (PR). The Kaplan-Meier method was used to derive the expected survival curves for patients in the treatment group.

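### Section 5.1.1 defines the response rate analysis population as responders only, which contradicts the ORR definition and the ITT denominator named elsewhere in the protocol

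*Protocol*

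**What the plan says.** Section 5.1.1 lists three populations.

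- Efficacy: "The efficacy analysis will be conducted in the intention-to-treat (ITT) population, defined as all patients who received at least 2 cycles of study drug therapy".
- Safety: every patient with at least one dose of study drug.
- Response rate: "The response rate analysis population refers to all patients in the ITT population who achieved partial or complete response", with response judged by RECIST.

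Section 5.1.3, which heads the efficacy analyses including the primary one, repeats the first assignment: "The efficacy analysis will be performed in the ITT population".

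The primary endpoint is ORR. Section 3.7.1 defines it as follows: "Objective response rate (ORR) refers to the proportion of patients whose tumors shrink to a certain extent and sustain this reduction for a specified duration". It then says that CR and PR are the qualifying responses. Section 5.1.3.1 gives the same definition in similar words.

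The sample-size text appears twice in the synopsis, in the rows on total number of cases and on statistical analysis. It is built on "assuming an ORR of 70% in this study and an ORR rate of 50% in the historical controls" and places this comparison in the ITT set, with a Simon two-stage design, one-sided alpha 0.05, power 0.8 and 37 patients.

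One analysis does use responders only. Section 3.7.1 says: "The duration of response maintenance was calculated for all patients who achieved confirmed RECIST-standardized PR or CR".

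**The concern.** A population for a response rate has to contain patients who could have responded and did not. The set in 5.1.1 excludes all of them, because a patient enters it by having a PR or CR. Numerator and denominator are then the same people.

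ORR is the sole primary endpoint, and its comparison with the 50% historical rate is what the 37 patients are sized for. The trial has a single arm and response is investigator-assessed, so a fixed and unambiguous denominator is one of the few safeguards available. Section 5.1.1 instead gives a general rule (efficacy in ITT) followed by a more specific set whose label points at the primary endpoint and whose content cannot serve it. A reader has to decide which sentence governs.

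This is not a detail left to a statistical analysis plan. The protocol has already defined the set, and a SAP that gave it a usable definition would depart from the protocol.

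**Working it through.** **Step 1. Reproduce the plan's own figure.** Inputs from the synopsis: p0 = 0.50, p1 = 0.70, one-sided alpha 0.05, power 0.80, Simon two-stage design. Exact binomial enumeration of two-stage designs gives these results:

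- Minimax design: stop if there are 12 or fewer responses in the first 23 patients; declare success with more than 23 responses in 37. Exact alpha is 0.0482 and power 0.8011.
- Optimal design: 8/15 at stage one and 26/43 overall, so 43 patients.

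The stated 37 therefore reproduces as the minimax design. The protocol does not print the boundaries; they are recovered here. As a cross-check, a single-stage rule of at least 24 responses in 37 gives alpha 0.0494 and power 0.807.

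**Step 2. Compute the rate in each set.** Let k be the number of responders and n = 37, assuming that all 37 patients are in the efficacy set.

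- Full set: rate = k/n.
- Set as defined in 5.1.1: rate = k/k, which is 1 for every k ≥ 1 and undefined for k = 0.

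| Responders k | Full set, k/37 | Responders-only set, k/k |
|---|---|---|
| 0 | 0% | undefined |
| 18 | 48.6% | 100% |
| 24 (lowest success count) | 64.9% | 100% |
| 26 (0.70 × 37 = 25.9) | 70.3% (exact 95% CI 53.0% to 84.1%) | 100% |

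**Step 3. Check whether the responders-only rate could carry information.** Even at the null rate of 50%, the probability of at least one responder is 1 − 0.5^37, which is above 0.9999. A rate in that set would be 100% almost surely whether the true rate were 50% or 70%, so it cannot distinguish the two. The criterion of at least 24 responses in 37 has meaning only over the full set.

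**Step 4. Compare the places in the protocol.**

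| Place | Set attached to response or efficacy |
|---|---|
| Synopsis, sample size | ITT, for the ORR comparison of 70% with 50% |
| 5.1.1, first sentence | ITT, for efficacy |
| 5.1.1, last sentence | ITT patients with PR or CR, labelled for response rate |
| 5.1.3 | ITT, for efficacy |
| 3.7.1 and 5.1.3.1 | ORR as a proportion of patients; no set named |
| 3.7.1, duration of response | Confirmed PR or CR |

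The last sentence of 5.1.1 is the outlier. No later section refers to that set. Its content matches only the duration-of-response analysis, apart from the word for confirmation, which 3.7.1 has and 5.1.1 lacks.

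**The case against.** The strongest objection is that nothing in the protocol tells anyone to compute ORR in this set. It is defined once and never used. Sections 5.1.1 and 5.1.3 assign efficacy to ITT, 5.1.3.1 sits under 5.1.3, and the synopsis ties the ORR hypothesis to ITT by name. The English also reads as a translation, and the sentence may simply be a mislabelled responder set intended for duration of response. On that view no plausible reported result changes.

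Most of this stands, and it limits the point. A reader might infer that the protocol fixes the primary ORR at 100%, or that 5.1.1 is the only place naming a population for the response rate. The documents support neither inference. The 100% arises only if the labelled set is used against the ITT sentences, and the synopsis names ITT for ORR. Nor is duration of response left without a set, since 3.7.1 describes one directly.

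What does not stand is the conclusion that nothing needs correcting. The label names the primary endpoint, the definition is incompatible with that endpoint, and no text gives the set another purpose. That it was meant for duration of response is a reasonable inference but remains one. Section 5.1.3.1 does not settle the matter, because it restates the endpoint without naming a denominator.

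**Conclusion.** The point holds as an internal contradiction about the denominator of the sole primary endpoint. The set that 5.1.1 labels for the response rate is selected on the outcome. It cannot yield a response rate, and it conflicts with the ORR definition and with the ITT set named for efficacy and for the sample size.

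If the set were used, the reported rate would be 100% at any true rate, for example 26/26 in place of 26/37 = 70.3%. That figure is conditional on the set being used, which the protocol does not direct, so it should not be read as the expected result. The 100% itself is an identity and needs no assumption. The 26 of 37 rests on the protocol's assumed 70% and on all 37 patients being in the efficacy set. N = 37, alpha, power and the recovered success count are unaffected.

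The requirement in 5.1.1 of at least two cycles for ITT membership is a separate matter. Correcting that requirement would leave this sentence still defining a responders-only set.

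**What to change.** 1. In 5.1.1, delete the response rate analysis population. Alternatively, rename it the duration-of-response population, align it with 3.7.1 (confirmed PR or CR), and state that it is used for that analysis only.
2. In 5.1.1 and 5.1.3.1, state that the ORR denominator is every patient in the efficacy population, responders and non-responders alike, with non-evaluable patients counted as non-responders.

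The cost is a few sentences of protocol wording, with no new patients, data or sample-size calculation. The second half of item 2 goes a little beyond removing the contradiction, but it is needed for the denominator to be a single fixed number. Its one downside is that the reported ORR may be slightly lower than if non-evaluable patients were dropped. As an illustration with assumed counts, 22 responders and 2 non-evaluable patients among 37 give 22/37 = 59.5% rather than 22/35 = 62.9%.

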5.1.2 Baseline and Demographic Characteristics

Summarize the baseline, demographic characteristics, baseline tumor characteristics, medical history, previous anticancer therapy, concomitant medications, vital signs, and trial discontinuation of all patients who underwent randomization according to different treatment groups. For continuous assessments, calculate the mean, standard deviation, range, and median; also calculate absolute values, frequencies, and percentages.

5.1.3 Efficacy Analysis

The efficacy analysis will be performed in the ITT population.

5.1.3.1 Primary Efficacy Analysis

The primary endpoint was the objective response rate (ORR). The objective response rate refers to the proportion of patients who achieved tumor shrinkage of a certain size and maintained it for a specified duration, including cases with complete response (CR) or partial response (PR). The Kaplan-Meier method was used to derive the expected survival curves for patients in the treatment group.

5.1.3.2 Secondary Efficacy Analysis

The depth of response (DpR) is defined as the percentage of maximum tumor shrinkage achieved during treatment compared to baseline. If a complete response (CR) is observed, the DpR is recorded as 100%.

Tumor response and disease progression will be assessed by investigators according to the RECIST criteria.

Progression-free survival (PFS) is defined as the time from randomization to tumor progression or death, with tumor progression recorded promptly.

Overall survival (OS) is defined as the time from randomization to death from any cause.

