3.6 Treatment Plan

3.6.1 Treatment Arrangements

Treatment regimen: Anlotinib, orally, 12 mg once daily, administered from day 1 to day 14 of each cycle, with each cycle lasting 3 weeks; Sintilimab, 200 mg, intravenous infusion for 1 hour \pm 5 minutes, administered every 3 weeks until disease progression or intolerable adverse reactions occur.

Treatment should be continued until disease progression or intolerance is achieved. Due to the inherent limitations of the RECIST criteria used for efficacy evaluation, if imaging suggests disease progression but the study physician determines that the patient has clinical benefit, treatment may still be continued.

The efficacy was evaluated every 6 weeks.

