3.7.3.1 Research Visits

- Screening visit should be conducted within 28 days prior to initiation of study drug therapy.
- The treatment period refers to the duration from the initiation of the first study drug administration until the patient discontinues the study drug therapy.
- Patients were evaluated every 8 weeks after discontinuation of study drug therapy due to non-progressive conditions. If disease progression was confirmed, they would enter the follow-up period. During this period, contact with patients should be maintained every 3 months until the patient's death was recorded, to collect data on overall survival.

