Efficacy Evaluation: All patients will undergo one of the following efficacy evaluations:

Complete remission (CR): All clinical and imaging evidence of the tumor (including target and non-target lesions) is eliminated.

Partial response (PR): A reduction of at least 30% in the sum of LD values at the target lesion compared to baseline total LD.

Stable Disease (SD): A stable state of the disease. The lesion has not met the PR criteria for shrinkage or has not met the PD criteria for progression.

Disease progression (PD): Referring to the minimum total LD value recorded from the start of treatment, the sum of LD in the measured lesions increases by at least 20% or one or more new lesions appear. The emergence of any new lesions indicates disease progression. In special cases, unmeasurable lesions with clear progression may also be accepted as evidence of disease progression.

Evaluation of therapeutic efficacy for target lesions versus non-target lesions

Target lesion	Non-target lesions	New lesion	Overall response	This type of optimal response also requires
CR	CR	not have	CR	Confirm after 4 weeks
CR	Non-CR/Non-PD	not have	PR	Confirm after 4 weeks
PR	Non-PD	not have	PR	
SD	Non-PD	not have	SD	At least 4 weeks from the baseline period
PD	any	Present or absent	PD	No SD, PR, or CR had occurred previously.
any	PD	Present or absent	PD	

any	any	have	PD	
-----	-----	------	----	--

Patients with an overall deterioration in health status requiring treatment discontinuation should be reported as 'symptom exacerbation' if there is no objective evidence of disease progression at this time. Objective disease progression should be observed and documented as closely as possible even after treatment cessation.

Relief time

The duration of remission should be calculated from the time of the first meeting of the criteria for CR or PR (whichever is recorded first) until the date of the first recorded disease recurrence or progression.

disease stable time

The duration of disease stability should be calculated from the start of treatment until disease progression is achieved, with the minimum measured lesion size after treatment initiation serving as the reference.

measuring method

The same evaluation criteria and measurement techniques should be used to describe and report each designated lesion during both the baseline and follow-up periods.

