7.5 Research Process Table

Flowchart of Therapy Process

	pretherapy	Each 3-week period constitutes one cycle.			Post-treatment follow-up visit	Follow-up after treatment discontinuation due to non-progressive conditions until disease progression	Follow-up after progression 9
		Cycle 1	Cycle 2	The 4th and subsequent cycles until disease progression or treatment discontinuation			
Operation item	Filter period	Day 1	Day 1	Day 1	Within 7 days	Every 8 weeks	Every 3 months
Informed Consent Form	X (within 28 days)						
Medical History 1	X (within 7 days)						
Complete physical examination 2	X (within 7 days)						
Inclusion/Exclusion Criteria	X						
stochastic	X						
Life signs and ECOG score	X	X	X	X	X	X	
12-lead electrocardiogram	X (within 28 days)		X	X	X		
Brain CT or MRI scan 3	X (within 28 days)						
Imaging Evaluation 4	X (within 28 days)			X (every 6 weeks) -----			
Hematological examination 5	X (within 7 days)		X	X	X		
Complete Set of Biochemical Tests 6	X (within 7 days)		X	X	X		
Urine test 7	X (within 7 days)		X	X	X		
Fecal Test 8	X (within 7 days)			X (every 6 weeks) -----			
Serum pregnancy test	X (within 7 days)						
Study of drug use		X	X	X	X		
Evaluation of Adverse Events (AEs)				-----(
comorbidities and concomitant medications				-----(

1. Complete medical history, demographic data, surgical history, concomitant medications, comorbidities, allergy history, and smoking history.
2. Complete physical examination, ECOG performance status score, height, weight, vital signs, and detailed examinations of all body systems.

3. Head CT/MRI scans are only required for patients with baseline neurological symptoms to exclude brain metastases.
4. Tumor assessment during the treatment phase is required every 6 weeks. After treatment completion, imaging evaluations are required every 8 weeks until disease progression occurs. If a patient withdraws from the study due to disease progression, no additional CT scans are required during the final follow-up at study completion.
5. Hematological tests include: hemoglobin, hematocrit, platelets, white blood cells, absolute neutrophil count, and absolute lymphocyte count, which can be performed 1 day prior to the start of each treatment course.

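### The depth-of-response window runs past RECIST progression whenever treatment does; best response for ORR has a narrower gap of the same kind

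*Protocol*

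**What the plan says.** **DpR.** Section 5.1.3.2 defines it as "the percentage of maximum tumor shrinkage achieved during treatment compared to baseline", with 100% recorded for a complete response. Section 3.7.1 gives the same definition.

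**Length of treatment.** Section 3.7.3.1: "The treatment period refers to the duration from the initiation of the first study drug administration until the patient discontinues the study drug therapy". The end point is stopping the drug, not progression.

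**Treatment past progression.** Section 3.6.1: "if imaging suggests disease progression but the study physician determines that the patient has clinical benefit, treatment may still be continued".

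**Scans.** Section 7.5, note 4: "Tumor assessment during the treatment phase is required every 6 weeks". Section 3.7.3.2 sets the same interval.

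**ORR.** Section 5.1.3.1 describes it as the "proportion of patients who achieved tumor shrinkage of a certain size and maintained it for a specified duration", counting CR and PR. It gives no assessment window.

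**Response rules.** Section 5.1.3.2: "Tumor response and disease progression will be assessed by investigators according to the RECIST criteria". Section 7.3 adds: "The emergence of any new lesions indicates disease progression". Its response table makes the overall result PD when there is a new lesion or non-target progression. For target-lesion PD, it makes PD the best response only if no SD, PR or CR came earlier. PR is measured against baseline and PD against the smallest sum recorded on treatment. Remission ends at the first recorded recurrence or progression.

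**The concern.** A patient kept on treatment after progression goes on producing tumour measurements. Under the DpR definition, a new minimum reached after progression replaces the earlier one. The patient's DpR then describes a tumour that had already failed the progression criterion used for PFS.

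The effect goes one way, because a maximum can only stay the same or rise as the window lengthens. It is also selective: it arises only in patients whom the physician chooses to keep on treatment, in a trial with investigator-assessed response and historical controls. If the same happens to best overall response, the primary endpoint is affected, and one patient can be both a responder for ORR and an earlier event for PFS.

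**Working it through.** **1. DpR: the sections side by side**

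- Window: during treatment (3.7.1, 5.1.3.2).
- Treatment ends: when study drug is stopped (3.7.3.1).
- Study drug may continue past imaging progression (3.6.1).
- Scans in the treatment phase: every 6 weeks (3.7.3.2, 7.5 note 4).
- Sentence closing the window at progression: none.

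So post-progression measurements fall inside the window. DpR changes only if one of them is below the pre-progression minimum. Shrinkage that merely reverses the regrowth changes nothing. New lesions do not limit DpR, because it is a percentage change and the overall-response table does not govern it.

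**2. ORR: what Section 7.3 blocks and what it leaves open**

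- Progression by a new lesion: overall PD while the lesion is present, however far the target lesions shrink. Blocked.
- Non-target progression: overall PD while it is present. Blocked.
- Target-lesion PD with no earlier SD, PR or CR: best response PD. Blocked.
- SD, then target-lesion PD, then shrinkage of at least 30% from baseline, with no new lesion and no non-target PD: fits the PR row. Not blocked.

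An invented example of the open path, in millimetres:

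| Assessment | Sum | Comparison | Result |
|---|---|---|---|
| Baseline | 100 | – | – |
| First | 90 | (100 − 90)/100 = 10% below baseline | SD |
| Second | 108 | (108 − 90)/90 = 20% above minimum | PD, PFS event |
| Third, still treated | 70 | (100 − 70)/100 = 30% below baseline | PR row met |

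DpR is 30% as written and 10% if the window closes at first progression. The patient could enter ORR as a responder although the PFS event came first. Remission, which ends at first recorded progression, would end before it began.

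**3. Size for ORR**

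Inputs from the protocol summary: p0 = 0.50, p1 = 0.70, one-sided alpha 0.05, power 0.80, Simon two-stage, N = 37. The stage sizes and cut-offs are not stated. An exact search gives a minimax design that reproduces N = 37: stop if 12 or fewer respond among the first 23; otherwise continue to 37 and reject if responses exceed 23.

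Rejection probability at response rate p:

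R(p) = Σ (x = 13 to 23) P(X1 = x | 23, p) × P(X2 ≥ 24 − x | 14, p)

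R(0.50) = 0.0482 and R(0.70) = 0.8011, so the stated error rates are met.

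Each patient counted only through a post-progression response adds 1/37 = 2.7 percentage points. The documents give no rate for this, so take k expected extra responders as an assumption, with a true ORR up to progression of 50%. The counted rate is p = 0.50 + k/37:

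| k (assumed) | p | R(p) |
|---|---|---|
| 0 | 0.500 | 0.048 |
| 0.5 | 0.514 | 0.067 |
| 1 | 0.527 | 0.091 |
| 2 | 0.554 | 0.157 |

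No comparable figure can be given for DpR: the protocol attaches no test or threshold to it and gives no rate of treatment past progression.

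**The case against.** Five points can be made against this.

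- **A reader might infer that nothing stops post-progression shrinkage from counting as a response.** The protocol does not support that. Response is judged by RECIST, and the table in Section 7.3 closes the new-lesion, non-target and first-result-PD routes. This stands, and it confines the ORR exposure to the single path above.
- **How best overall response is derived is commonly left to a SAP, and none is shown.** For ORR this has force: the gap is an absent sentence. It has less force for DpR, where the protocol states a window that a SAP would have to override.
- **No passage says that DpR must stop at progression.** True; closing the window there is an analysis preference. But the present window lets continuation decisions change the endpoint and puts DpR out of step with PFS.
- **Scans after progression are not certain.** Section 3.6.1 makes continuation an exception, the treatment column in Section 7.5 ends at progression or treatment discontinuation, and the post-progression column shows no imaging. Against that, Section 3.7.3.1 and note 4 of Section 7.5 tie six-weekly assessment to the treatment phase. How many such scans there will be is unknown.
- **The false-positive figures rest on nothing in the documents.** The number of late responders is assumed and the decision rule is derived. This stands; they show sensitivity only.

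**Conclusion.** The point holds for DpR as written: post-progression shrinkage counts whenever it passes the earlier minimum. This depends only on the protocol's own definitions and on some patients being treated and scanned past progression. DpR is a secondary endpoint with no decision attached, so the consequence is modest.

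For ORR the point holds only for SD followed by target-lesion PD followed by at least 30% shrinkage from baseline. The cost is 2.7 points of ORR per patient. The false-positive range of 0.067 to 0.157, against 0.048, is illustrative. It assumes 0.5 to 2 expected extra responders, a true ORR of 50% and the derived minimax rule; it should not be read as the trial's actual error rate. The sample size of 37 is unaffected. Overall this is a low-severity point, worth making because the correction is cheap.

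**What to change.** In Sections 3.7.1, 5.1.3.1 and 5.1.3.2, state that DpR and best overall response use only assessments from baseline up to and including the first RECIST progression or the start of new anticancer therapy, whichever comes first. Add that shrinkage recorded later is reported descriptively and enters neither endpoint.

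The new-therapy clause adds little for DpR, since Section 3.6.3.1 already bars other anticancer drugs alongside study treatment. It is more useful for ORR, which has no stated window and whose patients may still be scanned after stopping treatment without progression.

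The cost is a couple of sentences and slightly less favourable DpR, and possibly ORR. Sample size, scan schedule and the provision on continuing treatment stay as they are.
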